6.4.2.7 GENERALISED ANXIETY DISORDER - 7 (GAD-7)

The GAD-7 is a patient assessed 7 question instrument to screen for generalised anxiety disorder. It incoroprates feeling on edge, not being able to control worrying, worrying too much about things, trouble relaxing, restlessness, irritability and feeling afraid.

6.4.2.8 EUROQOL (EQ-5D-5L)

The EQ-5D-5L is a 5-item participant self-report measure that assesses the health status in terms of five dimensions: mobility, self-care, usual activities, pain/ discomfort and anxiety/ depression.

6.4.2.9 TOPICAL TREATMENTS

At baseline, months 1, 3 and 6, participants will be asked about their current use of topical eczema treatments.

6.4.3 SKIN PHOTOGRAPHY

Participants will be asked to optionally consent to have photographs of their skin taken at baseline and at month 6 on a camera or mobile phone (according to standard practice for clinical photography at individual hospital sites). A standard set of photographs will be taken by a member of the research team with appropriate training and following a standard operating procedure.

6.5 SAFETY DATA

6.5.1 PHYSICAL EXAM

The general physical examination will be conducted by a qualified physician at screening and baseline according to routine clinical care. The extent of subsequent examinations will be at the discretion of the physician, as clinically indicated. Any examinations not required should be recorded as 'not done'.

6.5.2 BLOOD PRESSURE

Blood pressure will be measured at screening and baseline. The need for any drug-specific additional safety assessment blood pressure readings is stated in the individual drug appendices
(Appendices 1-4). Blood pressure should be measured in an upright position after the participant has been rested for five minutes

6.5.3 ADVERSE EVENTS

During each visit, participants will be asked about adverse events (see section 10). All adverse events will be recorded in an ongoing adverse event log stating start/ end date, severity, serious adverse event, relatedness to study medication, relatedness to study procedure, impact on treatment and outcome. Adverse events of special interest will be captured in more detail (see section 10.2).

6.5.4 CONCOMITANT MEDICATIONS

During each visit, participants will be asked about their current medication. All concomitant medication will be recorded in an ongoing concomitant medication log.

6.5.5 DOSE INCREMENTS AND THERAPEUTIC SWITCHES

All dose increments or reductions will be recorded with any corresponding clinical reason/ comment. All treatment switches (as per the pre-defined 6 month switch criteria) will be recorded with corresponding clinical reason/ relevant comment (see section 7 Interventions).

6.5.6 WITHDRAWAL

A withdrawal form must be completed in the event of participant death or at month 12 or where the participant has stopped taking study medication and is no longer prepared to provide any follow up data. Every effort will be made to continue data collection for participants who stop taking study medication. Where the participant has stopped study medication but is still being followed for outcome data, a withdrawal form should not be completed, but a status update must be recorded in the eCRF every 3 months as documented in section 5.5.

6.6 **TREATMENT ADHERENCE**

6.6.1 VISUAL ANALOG SCALE FOR MEDICATION ADHERENCE (VAS)

The VAS for medication adherence was developed as an adjunct self-report measure of medication adherence³⁴. The VAS asks individuals to mark a line at the point along a continuum showing how much of each drug they have taken in the past 3 months.

6.7 LABORATORY DATA

All tests listed below will be performed as per the time points indicated in the participant timeline in section Table 1 (Section 2, Study Design). In addition, laboratory safety tests may be performed at unscheduled times, if deemed necessary by the investigator and abnormal results recorded as an adverse event if clinically significant. Trial sites will use the routine local laboratories. If samples are requested elsewhere (eg via a community based doctor) the laboratory results report should be requested. Results must be reviewed and signed by a physician, the local PI is responsible for ensuring appropriate documentation. After consent is obtained, clinically significant abnormal laboratory results will be recorded in the adverse events log. Individual result values will not be transcribed to the eCRF unless outside the normal range.

Blood samples for methotrexate polyglutamate and filaggrin analysis will be sent to the KCL 9th floor St John's Institute of Dermatology Laboratory, Guy's Hospital, for processing – see sample flow diagrams (Appendix 7) and lab manual for logistical arrangements and sample analysis plans. Where optional consent is provided by participants, there will be long term storage of DNA samples in the

St John's Research Tissue Bank (part of Guy's Research Tissue Bank, Ethics Committee ref: 07/H10712/106; HTA License Number 12521).

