3.3 EXPLORATORY OBJECTIVES

- 1. Provide data on whether the carriage of filaggrin gene mutations (one or two) associates with treatment response (possible predictive biomarker).
- 2. Provide data on whether methotrexate polyglutamate measurement can be used as a biomarker for treatment response on methotrexate.
- 3. Examine whether baseline IgE and eosinophil levels are predictors of outcome on the different therapies.

- 4. Examine whether predominant head and neck ("exposed site") eczema at baseline is a predictor of outcome on the different therapies.
- 5. Explore patient thoughts about participating in the trial, expectations of treatment, experience in the trial, experience on specific treatments and suggestions relating to the future implementation of these therapies in practice.
- 6. To assess the utility of photographs for monitoring eczema through deep learning-based severity assessments and accrue a comprehensive collection of photographs of skin, thereby establishing a critical resource for future use by investigators to improve outcomes in eczema.

4 **OUTCOME MEASURES**

4.1 **PRIMARY OUTCOME**

Objective eczema severity using EASI²⁴ (blinded assessment at 6 months, presented as mean absolute change from baseline).

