6.7.1 BLOOD TESTS

6.7.1.1 SCREENING BLOODS

Serology (as per local practice) HIV Hepatitis B and C IgE Interferon-gamma release assay (IGRA) – e.g. T-SPOT* VZV (if no history of chicken pox)

HAEMATOLOGY Haemoglobin Haematocrit Total and differential leukocyte count Red blood cell count Platelet count

BIOCHEMISTRY

Creatinine Potassium Liver function tests (LFTs) Lipids Urate Creatinine kinase

* TB screening should be performed as per local guidance at individual sites (**but blood testing is an essential requirement**)

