12.9 METHODS FOR ADDITIONAL ANALYSES (E.G. SUBGROUP ANALYSES)

For subgroup analysis (moderate and severe groups), treatment effect estimates will be estimated for each subgroup and formally tested by including an interaction between subgroup and treatment as a fixed effect in the analysis models.

In a secondary analysis, to identify the optimal treatment pathways adjusting for non-responders who switch treatments, we will use Q-learning to identify the pathway that maximises the expectation of the outcomes at 12 months, and if these differ by patient characteristics. Q-learning is a popular, regression-based approach for estimating treatment pathways involving treatment switching over time, as is permitted in this study after 6 months for non-responders. It involves defining the quality of treatment functions (Q-functions) at each time point. For the clinician-assessed eczema severity (EASI) outcome at 1 year, this is the expectation of the outcome conditional on treatment and covariate history from 6 months and baseline, estimated through linear regression. The maximum argument of the expectation with respect to the choice of treatments at 6 months is then regressed on the baseline randomisations and covariates. The optimal treatment pathway for an individual is then defined as the pathway that maximises the Q-function at both time points, and this will be estimated for different subgroups of participants.

We will additionally explore whether the carriage of filaggrin-null mutations, baseline IgE and eosinophils and predominant head and neck eczema predicts treatment response on the three treatments and whether methotrexate polyglutamate measurement can be used as a biomarker for treatment response in those on methotrexate.

If two comparators (A, B) are both found to be superior to the current control (C) in each respective pair-wise comparison, we may make a direct comparison between A and B. There is limited power for such a comparison, and the results of this direct comparison will be presented as opportunistic and exploratory. Only participants that could have been randomised to both A and B will be included in this opportunistic comparison (i.e., will exclude participants that were contraindicated to 1 or both arms, and will exclude participants that were randomised when 1 arm was not yet available).

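### Section 6.7 keeps in-range screening IgE and eosinophil values out of the eCRF, although exploratory objective 3 and section 12.9 use both as predictors

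*Protocol*

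**What the plan says.** Protocol section 6.7 opens by setting its scope: "All tests listed below will be performed as per the time points indicated in the participant timeline". It adds that "Trial sites will use the routine local laboratories" and then fixes what reaches the trial database: "Individual result values will not be transcribed to the eCRF unless outside the normal range". The tests below it include the screening bloods in 6.7.1.1. IgE is there under serology, and the haematology panel has "Total and differential leukocyte count", which is where the eosinophil count comes from.

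Exploratory objective 3 (section 3.3, repeated in the synopsis) is: "Examine whether baseline IgE and eosinophil levels are predictors of outcome on the different therapies". Section 12.9 plans to explore whether "baseline IgE and eosinophils and predominant head and neck eczema predicts treatment response". Section 1.2 also names the two markers among the factors to be examined as stratifiers of response.

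**The concern.** A rule that records only abnormal results suits safety bloods, where the normal result carries little information. It does not suit a predictor. To relate outcome to the level of a marker, or to ask whether that relation differs between arms, the analyst needs the numbers at the normal end as well as the raised end. Here the number is withheld because of its own value, at a threshold set by each site's laboratory. This is a data-capture rule, so an analysis plan cannot restore values that were never entered. At stake is how much the trial can say under exploratory objective 3. The primary and secondary analyses do not use these values.

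**Working it through.** The protocol states no figure on this point, so there is none to reproduce. The check has two parts.

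**1. Do the values reach any dataset?** Section 9 lists five datasets.

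- Macro eCRF: subject to the 6.7 rule, with no exemption for IgE or the differential count.
- Randomisation system (8.3.3): initials, date of birth and stratifiers.
- DrDoctor (9.2): patient-reported outcomes.
- CAPTURE: section 6.2.4 speaks of clinical as well as sample data, but the itemised contents in 9.3 are demographics, study ID, visit date, samples collected and their use. No IgE or eosinophil result is listed.
- Photography database (9.4): images.

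The two other laboratory markers, methotrexate polyglutamate and filaggrin, have their own sample and analysis pathway (6.7 and Appendix 7). IgE and eosinophils have none, so on the text the in-range numbers are held only in site records.

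**2. What does that cost?** The share f of participants with an in-range value is not in the documents. I assume f = 20%, 40% or 50%; at 536 participants, 20% to 50% is 107 to 268 people. Further assumptions are a marker that is standard normal on the log scale, one common upper limit c with Φ(c) = f, and every out-of-range value lying above c. Let φ be the normal density at c. Information for a linear slope is expressed relative to recording every value (= 1).

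- (a) In-range participants dropped: (1 − f) × V, with L = φ/(1 − f) and V = 1 + cL − L².
- (b) Normal/raised split only: φ²/[f(1 − f)].
- (c) Raised values kept as numbers, in-range participants placed at the mean expected below c: 1 − f × V₀, with L₀ = φ/f and V₀ = 1 − cL₀ − L₀².

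With f = 20%: c = −0.842 and φ = 0.280.

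- (a) L = 0.350 and V = 1 − 0.295 − 0.122 = 0.583, so 0.8 × 0.583 = 0.47.
- (b) 0.0784/0.16 = 0.49.
- (c) L₀ = 1.400 and V₀ = 1 + 1.178 − 1.960 = 0.219, so 1 − 0.2 × 0.219 = 0.96.

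| In-range share | (a) dropped | (b) split | (c) censoring modelled |
|---|---|---|---|
| 20% | 47% | 49% | 96% |
| 40% | 25% | 62% | 88% |
| 50% | 18% | 64% | 82% |

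By the variance decomposition (c) should equal (a) + (b), and it does within rounding: 47 + 49 = 96, 25 + 62 ≈ 88, 18 + 64 = 82.

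A simulation of the complete-case analysis, case (a), puts this in terms of power for an arm-by-marker interaction. It used 107 evaluable per arm (134 × 0.8), an interaction slope of 0.4 residual SD per marker SD, two-sided 5% and 3,000 runs. Power was 0.84 with every value recorded, and 0.50, 0.31 and 0.18 with 20%, 40% and 60% in range. The mean estimated slope stayed at 0.39 to 0.40 against the true 0.40, so under a correct linear model the loss is in precision, not bias.

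**The case against.** The strongest counter-argument is that a blank is informative. Under the 6.7 rule, a test that was done and has no entered value was in range, so the value is left-censored at the local limit and not lost. Section 6.1.3 requires a physician to review laboratory results before randomisation, which makes that reading usually defensible. A normal/raised comparison remains possible, and a model for the censoring recovers most of the slope information (column c).

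Much of this stands. A reader might infer from the rule that the predictor analysis could run only in participants with raised values, that the loss in column (a) is what the rule produces, or that the result would not apply to the trial population. The documents support none of these. Dropping in-range participants is an analysis choice that the protocol does not prescribe. Nor does anything in the protocol say that a differential effect would lie at the low end of either marker. A reader might also point to the mean imputation in section 12.10. It is written for incomplete baseline covariates in the outcome models, not for values withheld by rule in an exploratory predictor analysis.

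Three further points are fair. Serology is left to local practice, so universal testing is less certain for IgE than for the differential count. The 6.7 sentence follows directly on adverse-event recording and may have been meant for safety results. The eCRF specification is not shown, so dedicated fields may exist.

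What the objection does not remove is this. The protocol nowhere says that a test done and in range is recorded as such, so a blank may not be distinguishable from a test not done, and with IgE left to local practice that matters. Column (c) needs a correct distributional model and known limits, which may vary by site. If dedicated fields do exist, 6.7 misdescribes practice and should be corrected anyway.

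**Conclusion.** The point holds as a conflict within the protocol: a capture rule that withholds in-range numbers is applied, without exemption, to two markers that the same document plans to use as predictors, by level in objective 3. The consequence is a loss of precision and range, not a demonstrated bias. Its size depends on an in-range share that the documents do not give and on how the blanks are handled. For 20% to 50% in range, between 18% and 96% of the slope information is kept, with the low figures applying only if in-range participants are discarded. Those figures assume a normal log-marker, a single limit, and the same share for both markers. Bias would become a concern if the relation is non-linear or if blanks are filled as though missing at random. Only an exploratory objective is touched, and the results should still be in site records, so the loss is avoidable. It is worth correcting because the correction is cheap.

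**What to change.** Add an exception to section 6.7 for the screening IgE and the absolute eosinophil count: enter the numeric value, units and local reference range in the eCRF for every participant tested, whatever the result, and mark the test as not done otherwise. Back-fill participants already randomised from source records before their data are locked; section 9.7.1 locks participants arm by arm, so this should be done before the first arm closes. If the eCRF already has these fields, only the wording of 6.7 needs to change.

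The cost is two extra eCRF entries, each with its units and range, and a short back-fill by sites. No new sample or visit is needed.

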6.7.1 BLOOD TESTS

6.7.1.1 SCREENING BLOODS

Serology (as per local practice) HIV Hepatitis B and C IgE Interferon-gamma release assay (IGRA) – e.g. T-SPOT* VZV (if no history of chicken pox)

HAEMATOLOGY Haemoglobin Haematocrit Total and differential leukocyte count Red blood cell count Platelet count

BIOCHEMISTRY

Creatinine Potassium Liver function tests (LFTs) Lipids Urate Creatinine kinase

* TB screening should be performed as per local guidance at individual sites (**but blood testing is an essential requirement**)

6.7.1.2 SAFETY BLOODS

The timing of post-randomisation drug-specific safety tests (including bloods, blood pressure and urinalysis) is shown in the main schedule of events (Table 1, section 2) and drug-specific schedules of events (at the beginning of each of the drug-specific appendices 1-4). The nature of drug-specific safety blood tests is detailed in the relevant drug appendices (section 1.4 in each appendix).

6.7.1.3 METHOTREXATE POLYGLUTAMATE LEVEL (MONTHS 1,3,6)

This is only required on those randomised to methotrexate. Please refer to the methotrexate-specific drug appendix (Appendix 2), section 1.4.4 for details.

6.7.1.4 BLOOD FOR DNA

All patients who consent for optional samples, at screening visit (collection at any visit permitted): 2 x 6ml of blood will be collected in EDTA Vacutanier tube (purple top) for DNA extraction to check FLG status and for future genomic interrogation. Please refer to lab manual for full procedure on how to collect, store and send samples.

6.7.2 URINALYSIS (BASELINE, MONTHS 1,3,6,9,12)

A urine protein: creatinine ratio is required at screening. This is only required as part of ongoing safety visits for those on ciclosporin. Please see Appendix 1 (ciclosporin-specific drug appendix) section 1.4.2.4 for timing and further details of required safety urinalysis.

6.7.2.1 URINE PREGNANCY TEST

Urine beta-hCG test will be used for the female participants of child-bearing potential during the baseline visit prior to randomisation to allow the site pharmacy adequate time to prepare the study medication for dispensing on the same day post-randomisation. The urine test beta-hCG test will be repeated at the 6-month visit only for female participants of child-bearing potential switching treatment from dupilumab or abrocitinib to methotrexate. Please refer to methotrexate-specific drug appendix (Appendix 2) section 1.4.3.3 for details.

IMP DOSING DATA 6.8

6.8.1 STUDY MEDICATION PRESCRIBED DOSE LOG

Study medication dosing, including any active temporary or permanent discontinuation of study medication, will be recorded on the Study Medication Prescribed Dose Log.

MEASURES TO PROMOTE PARTICIPANT RETENTION 6.9

Where possible data collection will be via routine follow up clinics, minimising the need for additional research visits. Much of the data are collected in routine care in recruiting sites and are not time consuming to complete. In the event a participant wishes to stop taking study medication, follow up visits should still be completed. Where appropriate, safety visits (blood sampling +/- blood pressure measurement) can happen remotely in the community. The week 30 safety assessment for those who switch on to methotrexate or dupilumab at 6 months could be remote (if easier for participant and local blood testing available in the community where needed).

7 INTERVENTIONS

7.1 CHOICE OF COMPARATORS

In the first iteration of the platform two different classes of systemic therapy (methotrexate and dupilumab) were tested against a control (ciclosporin). Abrocitinib is the first new treatment arm to enter the platform and has been included as an exemplar of the new class of JAK inhibitors licensed for and increasingly used to treat adult atopic eczema.

Further treatments and arms will be added in future amendments. The Trial Management Group (TMG) are responsible for proposing those treatments and related dosing to the Trial Steering Committee (TSC) for ratification.

Patients will be randomised 1:1:1:1 to one of the following trial arms:

- 1. Ciclosporin (PO)
- 2. Methotrexate (SC)
- 3. Dupilumab (SC)
- 4. Abrocitinib (PO)

For detailed information on each IMP please refer to the relevant individual drug appendix (Appendices 1-4). Information regarding side effects and administration is provided in those appendices and in the Participant Information Sheet (PIS).

7.2 INTERVENTION AND COMPARATOR DESCRIPTION, DOSING, PACKAGING, LABELLING, STORAGE AND ACCOUNTABILITY

Sites should not randomise patients unless they have sufficient drug available on site for all trial arms.

Investigators will be encouraged to adhere to the suggested dose increases for ciclosporin and methotrexate, but changes of dose outside of this schedule where clinically indicated will be permitted and recorded.

Dispensed trial medicines will be collected from pharmacy by the patient or their representative. At the baseline visit, the research team will train the patient on how to administer their new treatment using either their dispensed medication or a dummy device and counsel them on the new medication.

Participants should start the medication the day of their baseline visit, but if that is not possible as soon as possible thereafter. If there is a delay of more than 2 weeks then the site must contact the BEACON team to clarify how to proceed.

7.3 DISCONTINUING ALLOCATED INTERVENTIONS

Participants may temporarily or permanently stop taking study drug at their discretion or that of the site investigator. In all cases every effort should be made to ensure follow up data is collected per protocol to the end of the trial, unless the participant is formally withdrawing from further data collection (see section 5.5). The clinical study report will include reasons for participants discontinuing study medication.

7.4 CONCOMITANT MEDICATIONS PERMITTED OR PROHIBITED DURING THE TRIAL

Topical corticosteroids and topical calcineurin inhibitors will be permitted throughout the trial as per standard practice.

Prohibited medication which will be deemed as reason for trial exclusion include:

- UV treatment (UVB, UVB TL01, PUVA, UVA1, tanning beds)
- Immunosuppressants/immunomodulatory agents e.g. prednisolone, azathioprine, mycophenolate mofetil, tacrolimus and Janus kinase (JAK) inhibitors
- Biological agents used for the treatment of inflammatory skin disease
- Medications listed as contraindicated in the Summary of Product Characteristics (SmPC) for the trial drug that the participant is on (or, where relevant, for a trial drug that they are due to switch to). The following contraindicated medications are listed in the current SmPC's for the IMPs on the Electronic Medicines Compendium (EMC), but investigators are advised to refer to the most up to date SmPC on the EMC when assessing a participant's concomitant medications:
 - Ciclosporin (Neoral oral solution / soft gelatin capsules, 15/09/2023): products containing *Hypericum perforatum* (St John's Wort); medicines that are substrates for the multidrug efflux transporter P-glycoprotein (P-gp) or the organic anion transporter proteins (OATP) and for which elevated plasma concentrations are associated with serious and/or life-threatening events, e.g., bosentan, dabigatran etexilate and

aliskiren. Investigators are advised to refer to the most up to date SmPC on EMC for a more comprehensive list of medications that utilise these pathways.

- Methotrexate (Metoject 15mg / 20mg solution for injection pre-filled pen, 18/09/2024): concurrent vaccination with live vaccines
- Dupilumab (Dupixent 300mg solution for injection pre-filled pen / syringe, 09/09/2024) and abrocitinib (Cibinqo 200mg film-coated tablets, 09/2024): no contraindicated medications listed

All other usual care therapy is allowed during the trial.

7.5 **PROVISIONS FOR POST-TRIAL CARE**

Patients on methotrexate or ciclosporin at trial end will be able to continue treatment where deemed appropriate by the PI. Patients on dupilumab or abrocitinib will be able to continue treatment where in line with NICE criteria (including participants who switched from methotrexate or ciclosporin to dupilumab at the 6 month stage and participants on dupilumab or abrocitinib throughout the trial who had received previous systemic therapy for eczema pre-trial (e.g. azathioprine, mycophenolate mofetil) or are contraindicated to standard systemic treatments/ it would be inappropriate to switch). Any participant who suffers harm from trial participation has access to all services and relevant compensation offered by their participating institution.

